6. BACKGROUND AND CONTEXT / RATIONALE

FACULTY OF LIFE SCIENCES AND EDUCATION
FACULTY ETHICS SUB GROUP APPLICATION FORM

Evidence suggests that up to 90% women in the UK will experience severe menopausal symptoms (Hunter et al., 2001). Despite this, it has been reported that few women will seek medical help, and most will not access treatment until their symptoms have become extremely bothersome (Constantine et al., 2016). Unfortunately, those that do seek treatment for menopause are likely to face barriers to effective healthcare, with some reports suggesting that many women struggle to adequately communicate the totality of their menopausal symptoms to health professionals (Ismail et al., 2016; Woods et al., 2015).

[name] recently conducted a systematic review (submitted for publication) which demonstrated that symptom monitoring reduced women's reports of menopausal symptoms, such as hot flushes, urinary incontinence, headaches, reduced libido, and depressed mood. The systematic review also demonstrated that symptom monitoring increased health awareness and facilitated patient-doctor communication, decision-making, and treatment goal setting, all of which are antecedents for improved medical treatment outcomes (Ha & Longnecker, 2010). In the randomised trials included in this review, however, symptom monitoring was used as a control intervention against which another intervention (e.g., paced respiration) was compared, and the findings of benefits in the symptom monitoring control group were largely under recognised and rarely discussed (Sternfeld et al., 2014; Carpenter et al., 2012).

7. AIMS AND OBJECTIVE(S) OF THE RESEARCH STUDY:

It is important to further our understanding of the extent to which symptom monitoring alone could be a useful intervention to support menopausal women. Should monitoring be beneficial, it has the potential to offer women a useful and economical way of improving their wellbeing when waiting for treatment, or for women who choose not to receive treatment for menopausal symptoms, or for whom medical treatment is contra-indicated. Thus, a randomised controlled trial (RCT) will be conducted in the proposed research because symptom monitoring as a stand-alone intervention for the menopause has not yet been evaluated experimentally.

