Participants in the intervention group will be invited to monitor their physical and emotional symptoms every day for 14-days using the Daily Record Keeping form (DRK; Boivin & Takefman, 1995), administered via JISC Online Surveys. **See Appendix 4 to view the daily DRK survey in Word document format. The online DRK survey can be viewed as it's presented on JISC Online Surveys via this link:** <https://southwales.onlinesurveys.ac.uk/daily-record-keeping-form-preview>. At 10am each day of the intervention period, participants in the intervention group will be sent an email asking them to complete the DRK survey by the end of the day- they will also receive text message reminders to complete the DRK at 5pm each day, unless they opt out of reminders. Both the email and text reminders will include a link to the online DRK. Participants can opt out of text message reminders at any time by emailing [name] requesting to opt out. Once participants have returned DRK surveys every day for 14 days, on the 15th day they will be asked to complete the follow-up survey within 24 hours. Once they have returned the follow-up survey they will be sent their £20 gift voucher via email. **See Appendix 5, page 1 to view a template of the daily DRK email reminders, see Appendix 5, page 2 to view a template of the text message reminders. See Appendix 6, page 1 to view the email template advising intervention group participants of their group allocation, and instructing them to complete the DRK survey each day for 14 days.** The online text messaging platform ClickSend will be used to manage the scheduling of daily text message (www.clicksend.com) See the section below titled "Data collection tools" for a more detailed explanation of the measures used in this study.

Control group:

Participants in the control group will not monitor their symptoms daily for 14-days and will instead be instructed to carry on as usual during the 2-week period, while the intervention group are monitoring. This group will complete all measures (including the DRK) at baseline and at follow-up on the 15th day only. **See Appendix 6, page 2 to view the email template advising control participants of their group allocation, and instructing them to carry on as usual for 14 days. If they indicated on the baseline survey that they are**

FACULTY OF LIFE SCIENCES AND EDUCATION FACULTY ETHICS SUB GROUP APPLICATION FORM

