Inclusion criteria: this study will involve adult females, who report at least 2 hot flushes per day, with self-reported peri- or post-menopausal status. Women taking menopause-specific treatments (e.g. HRT or anti-depressants) are included in this study provided they reach the criteria for hot flushes and are otherwise healthy.

Exclusion criteria: participants will be screened out of the survey if they answer no to the following questions, which will be presented before the information sheet, consent form and main survey: "Are you over the age of 18?", "Are you experiencing at least 2 hot flushes per day?", and "Are you experiencing either perimenopause or menopause?"

Additionally, care will be taken to identify and exclude outliers from analyses, especially when considering the data of those who say they have been diagnosed with chronic or severe conditions with symptoms overlapping with menopausal symptoms, including chronic fatigue syndrome, fibromyalgia, cancer, heart

**FACULTY OF LIFE SCIENCES AND EDUCATION
FACULTY ETHICS SUB GROUP APPLICATION FORM**

disease, thyroid disorders, depression and other mental illnesses. As the research team is not medically trained, we are not able to ascertain definitively if women do have any medical conditions. However, women will be informed in the information sheet that they should not participate if they have these conditions for the reason stated above, and those who report such conditions in the demographic and medical history will be statistically assessed with caution using univariate and multivariate analyses, and data from these individuals will be excluded where necessary. Participants who do not complete all study materials or comply fully with the experimental protocol will also be excluded from analyses. Participants who report demographic characteristics that have been related to poorer health will also be assessed as covariates. Differences in symptoms between groups according to employment status, living status and relationship status will be analysed to understand variances in health between these groups. This is because unemployed, or single, or individuals who live alone are more likely to report poorer health than others.

Power analysis:

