An a priori power analysis was conducted using G*Power 3 (Faul, Erdfelder, Lang, & Buchner, 2007) to test the difference between two independent group means (accounting for special, main effects, and interactions) using a two-tailed test, a medium effect size ($d = .40$) and an alpha of .05. Results suggested that a total sample of 52 participants with two equal sized groups of 26 was required to achieve a power of .80.

Medium effect sizes were estimated based on Cohen's (1962) conventional values because these values were derived from studies specific to psychological research (Aguinis, & Harden, 2009). Furthermore, medium effect estimates, rather than small estimates, were used for this research because this study is exploratory and small effects on symptom frequency might not be noticeable to participants. Small effects might imply that symptom monitoring as an intervention to help reduce menopausal symptoms may lack meaningful benefit.

Hoerger (2010) found evidence that at least 10% of participants will drop out of internet mediated research and such studies have high attrition rates. Furthermore, several studies have provided data on attrition rates of studies which employ a 2-week intervention period. Lancastle and Boivin's (2008) feasibility study aimed to establish whether a brief coping intervention (positive reappraisal coping intervention; PRCI) was acceptable and practical when evaluated in the context of a randomised trial. Of the 84 women who agreed to participate in the study 55 (65.5%) completed all measures, suggesting an attrition rate of 34.5%. Moreover, Lancastle's (2006) study also evaluated the PRCI alongside a positive mood inductive intervention, and a daily monitoring control group; this research reported a 31% attrition rate.

Therefore, taking into account average attrition rates from internet mediated research (10%), as well as studies which have utilised a 2-week intervention period (33%), it was decided that the proposed study will use a total sample of 78 participants with two equal groups of 39.

11. HAVE NATIONALLY APPROVED / REGULATORY BODY GUIDELINES BEEN FOLLOWED IN PREPARING THIS PROTOCOL?

(E.g. Association of the British Pharmaceutical Industry Guidelines (1983), Royal College of Physicians Guidelines, The Declaration of Helsinki, British Psychological Society guidelines, BERA, etc.). If so, please specify.

- Faculty of Life Sciences and Education Ethics Committee

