Appendix 14: The risk assessment table. [Page 98](#)

Appendix 1: The baseline survey in Word document format:

FACULTY OF LIFE SCIENCES AND EDUCATION
FACULTY ETHICS SUB GROUP APPLICATION FORM

Baseline questionnaire

Demographics:

4. Please type your email address (this is required to continue with this study)

.....

5. How would you describe your physical and mental health in general?

- Good
- Okay
- Poor

6. What is your living status?

- I live alone
- I live with my family
- I live with friends
- I live with my partner
- I live in shared housing
- I live in a residential home

7. What is your relationship status?

- In a relationship
- In a relationship and living together
- Married
- Divorced or separated
- Widowed
- Single

8. What is your current occupation? Tick as many as apply:

- Working full-time
- Working part-time
- Student
- Military
- Volunteer
- Looking for work
- Homemaker
- Retired

**FACULTY OF LIFE SCIENCES AND EDUCATION
FACULTY ETHICS SUB GROUP APPLICATION FORM**

- Unable to work due to illness or disability
- Full-time carer for a family member/ loved one
- Other

8b. If you selected Other, please specify:

.....

9. What is your ethnicity?

- White
- Asian
- Black
- Mixed ethnicity
- Other

9a. If you selected Other, please specify:

.....

10. What was the date of your last menstrual period? If you can't remember exactly please give your best estimate:

.....

11. Please type the name of the country and the town/city you live in:

.....

12. Are you currently using any medication or treatments for your menopause symptoms?

- No
- Yes

12a. If you selected Yes, please specify which medication or treatments you are using. Examples can include HRT, antidepressants, psychological treatments, counselling, or supplements.

.....

13. Please describe any health conditions that you are currently being treated for:

.....

**FACULTY OF LIFE SCIENCES AND EDUCATION
FACULTY ETHICS SUB GROUP APPLICATION FORM**

14. Please describe any non-menopause-related medications or treatments you are currently using:

.....

You are now going to be asked some questions about your health and you as a person, please work through them, giving the answer that best applies to you for each question.

Mood questionnaire:

15. Describe yourself as you generally are now, not as you wish to be in the future. Describe yourself as you honestly see yourself, in relation to other women of your age. Indicate for each statement whether it is:

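### Menopause treatment is recorded at baseline but used in no planned analysis, so the result averages over treated and untreated women and gives no estimate for the women named in the rationale

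*Combined protocol and SAP*

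**What the plan says.** **Rationale and objective.** Section 7 says that monitoring, if beneficial, could help women "when waiting for treatment, or for women who choose not to receive treatment for menopausal symptoms, or for whom medical treatment is contra-indicated". It adds that monitoring has not been tested experimentally as an intervention in its own right. The primary objective in the same section covers menopausal women, with no limit by treatment. The summary of objectives and the hypotheses in section 8 add none.

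**Who enters.** Section 10, inclusion criteria: "Women taking menopause-specific treatments (e.g. HRT or anti-depressants) are included in this study provided they reach the criteria for hot flushes", with the further condition that they are otherwise healthy.

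**Comparator.** Section 8 calls the control group usual care. Controls "will instead be instructed to carry on as usual during the 2-week period", so a treated control may simply continue her treatment.

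**What is recorded.** Section 9 lists current medications among the baseline variables. Item 12 of the baseline survey (Appendix 1) asks: "Are you currently using any medication or treatments for your menopause symptoms". Item 12a asks which, and its examples run from HRT and antidepressants to psychological treatments, counselling and supplements.

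**What is used.** Section 10 allocates from one list of 39 numbers out of 78, without stratification. The factors it names for covariate assessment are employment, living and relationship status. Section 7 names neuroticism and coping style as moderators. The ANOVA, regressions and correlations in section 22 do not name treatment.

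**The concern.** The women in the rationale are largely defined by not having medical treatment, yet treated women can fall in either arm and are never separated in the analysis. The trial therefore estimates monitoring plus usual care against usual care alone, averaged over whatever mix happens to enrol.

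Three things are at stake. First, a reader could carry the pooled result over to women awaiting or declining treatment, for whom the plan provides no estimate. Second, current treatment may well predict how symptoms move over two weeks. With arms this small and no stratification, a chance imbalance would go unadjusted. Third, section 7 says it matters to learn for whom monitoring helps, but the factor closest to its own list of beneficiaries is not among those examined. If treatment status is first examined after the results are known, the analysis will be post hoc.

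**Working it through.** **1. The plan's own sample size.** Section 10 sizes the trial "using a two-tailed test, a medium effect size ($d = .40$) and an alpha of .05" and concludes that "a total sample of 52 participants with two equal sized groups of 26 was required to achieve a power of .80". For two independent means, d = 0.40, two-sided 0.05 and 80% power, the noncentral t gives 100 per arm, not 26. Reading .40 as Cohen's f (d = 0.80) gives exactly 26 per arm. Power with 26 per arm is 0.29 at d = 0.40 and 0.81 at d = 0.80. The attrition step reproduces: 52 / (1 − 0.33) = 77.6, so 78. A calculation that starts from both d = .40 and 80% power therefore has no consistent base.

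**2. Size of the untreated subset.** The documents give no treated share q, so a range is assumed. Untreated women per arm among the planned completers = 26 × (1 − q), rounded. The 95% half-width, in SDs of the analysed outcome, is t × √(2/n) on 2n − 2 degrees of freedom.

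| q (assumed) | untreated n per arm | t × √(2/n) | half-width |
|---|---|---|---|
| 0 | 26 | 2.009 × 0.277 | 0.56 |
| 10% | 23 | 2.015 × 0.295 | 0.59 |
| 20% | 21 | 2.021 × 0.309 | 0.62 |
| 30% | 18 | 2.032 × 0.333 | 0.68 |
| 50% | 13 | 2.064 × 0.392 | 0.81 |

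**3. Chance imbalance without stratification.** Suppose 5, 10, 16 or 26 of the 52 completers are treated (about 10%, 20%, 30%, 50%). The hypergeometric chance that the treated share differs between arms of 26 by at least 15 points (four women or more) is 5%, 29%, 37% or 41%. The first is low because five treated women can only reach that gap if all fall in one arm. A four-woman gap, 4/26 = 15.4 points, shifts the unadjusted group × time contrast by 0.154 times the treated–untreated difference in change. If that difference were 0.5 SD (an assumption), the shift would be 0.08 SD. It averages to zero over randomisations.

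**4. Dilution, purely illustrative.** With e the effect in treated women relative to untreated, pooled effect = untreated effect × [1 − q(1 − e)]. If e = 1 the factor is 1 and nothing is lost. Power with 26 per arm, for q = 10%, 20%, 30%, 50%:

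- untreated d = 0.80, e = 0: 0.72, 0.62, 0.51, 0.29
- untreated d = 0.80, e = 0.5: 0.77, 0.72, 0.67, 0.56
- untreated d = 0.40, e = 0: 0.25, 0.20, 0.17, 0.11, from a start of 0.29

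The documents supply neither q nor e, so none of these is an expected loss.

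**5. A formal interaction test.** Standard error = √[2/(26(1 − q)) + 2/(26q)], which is 0.69 SD at q = 20% and 0.55 SD at q = 50%. Power to detect an interaction of 0.80 SD is 0.21 and 0.30 respectively.

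**The case against.** The case for leaving the plan alone is substantial.

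- **The objective is general.** The three groups appear in a conditional sentence about possible benefit, while the objective, its summary and the hypotheses concern menopausal women without restriction. Eligibility and a usual-care comparator fit that. A reader might infer that the trial answers the wrong question, but this would put a sentence of the rationale in place of the objective.
- **Stand-alone need not mean untreated.** The preceding background explains that earlier trials used monitoring as the control for something else. The natural reading is that monitoring is now the intervention under test.
- **The covariate list is not worded as closed.** Section 10 also speaks of demographic characteristics linked to poorer health, and section 9 places medications under demographic variables.
- **The groups named are not identical with a *No* to item 12.** A woman awaiting HRT who takes supplements would answer *Yes*.
- **Effect modification is unproven.** Treated women must still have at least two hot flushes a day.
- **Subgroup results will be imprecise,** as steps 2 and 5 show.

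All of this stands, and it limits the point. It does not supply the missing analysis: treatment is named in no model, and an open-ended covariate list is not pre-specification. Imprecision argues for estimates rather than tests, not for silence.

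**Conclusion.** The point holds as one of applicability and adjustment, not of bias. The treatment mix leaves the randomised comparison unbiased for menopausal women under usual care. What is missing is adjustment for a likely prognostic factor, an estimate for women without medical treatment, and a statement of the population to which the main result applies.

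A reader might also infer that enrolling treated women costs the trial a definite amount of power. The documents do not support that. The treated share and any difference in effect are unknown, the loss is zero if effects are equal, and the stated d = .40 does not give 80% power with 26 per arm in the first place.

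What can be sized is the precision of the missing estimate: about 23 down to 13 untreated women per arm, with half-widths of about 0.59 to 0.81 SD. This assumes 52 completers and a treated share of 10% to 50%, spread evenly between arms. That treatment is prognostic for two-week change is a reasonable expectation, not something the documents show.

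**What to change.** Keep the eligibility criteria. Before outcome data are examined, amend section 22 as follows.

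1. Add baseline menopause treatment as a covariate in the main symptom model so that it acts on follow-up or change. Either analyse follow-up with baseline and treatment as covariates, or include a treatment × time term in the mixed ANOVA. A covariate that enters only the between-subjects part would leave the group × time contrast untouched.
2. Define the classification from the free text in item 12a, blind to outcome, so that women using only supplements or counselling are not automatically counted as medically treated.
3. Pre-specify the monitoring-minus-control difference with its 95% interval by treatment status, as description and without further significance tests.
4. State that the main estimate applies to a mixed treated and untreated population under usual care, and that statements about untreated women are exploratory.

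The data are already collected. The cost is SAP wording, a short coding rule, one degree of freedom and subgroup intervals that will be wide.
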